### **6.4 Study Coordination**

When a prospective subject is identified by the appointment schedulers, consultants, audiologists or research team, the research team will be notified. A member of the study team will provide information about the study to the subject and will serve as the point of contact for the subject. A member of the study team will help organize the administration and receipt of surveys, as well as coordinate appointment visits. They will allot for breaks in between separate tests for patient comfort.

## **7 DATA COLLECTION AND ANALYSIS**

### **7.1 Data to Be Collected**

Demographic data to be collected will include patient's age, sex, medical comorbidities, current medications and medications taken within the last year, preoperative THI, TFI, Tinnitus VAS-A and VAS-L, GAD7, PHQ8, GHQ and NEO PI-R.

The patient will complete the THI, TFI and Tinnitus VAS-A and VAS-L immediately prior to stimulation, during stimulation, and following completion of stimulation at 10-minutes, 1-hour, 24-hours, 48-hours, and 1-week (or prior to the next scheduled session of promontory stimulation, whichever occurs sooner) following completion of stimulation.

## 7.2 Data Analysis

### a Power Analysis

Assuming the power was 80% and a **one** sided alpha of .05; we sought to determine a power analysis to detect a clinically significant decrease in tinnitus symptoms [3,12].

True Change in THI	SD of Change of THI	Sample Size		
		Equality	Superiority using 7 as bottom threshold	Superiority using 5 as bottom threshold
7	10	11		156
7	15	22		350
7	20	38		619
10	10	6	71	27
10	15	12	156	58
10	20	19	277	101
15	10	4	12	8
15	15	4	24	16
15	20	6	41	27

There are three different types of analysis used above to calculate sample size.

The first analysis shown is an equality test which assesses whether the mean change in THI level is different from zero. This is the simplest power calculation and is usually associated with a t-test. In our research question, we would like to consider the procedure a success if the scores improve significantly by a certain amount. This test only examines that, if the true change is 7 (10), it is different from zero.

The second two analyses seek to quantify the amount of change in THI we would like to consider clinically relevant. If we believe a clinically relevant change is 7 points on the THI scale we want to ensure that we have sufficient sample size to detect a mean change at or higher than 7. The final sample size column is less stringent in the mean we have to detect to consider the treatment a success, with requiring only a 5 point change to be clinically relevant (the threshold for not improving in the paper above).

The power calculation suggests that if we believe our true mean change to be a 15 THI points with a SD of 15, a difference greater than or equal to 5 can be detected using 16 subjects, while if we want to **detect a mean change greater than 7 we would need 24 subjects.**

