## **STUDY SUMMARY**

Title: Cochlear Promontory Stimulation for Treatment of Tinnitus: Towards Developing an Implantable Device

IRB Protocol Number: 17-004832

Methodology: Prospective, investigational

Target subject accrual: 100

Expected duration of study: 10 years

Subject participation duration: 4 days [3 sequential clinic visits scheduled 7 days (+14/- 2 days) apart with a 3 month follow up visit]

Primary Objective: Use of a cochlear promontory stimulation electrode to provide safe, short term relief of tinnitus.

Secondary Objective: Map the optimum regions of the cochlear promontory in planning for an implantable electrical device for long term tinnitus suppression.

Principal Investigator: [name]

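### Do the undersized Equality entries in the power table call for a change to the plan?

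*Combined protocol and SAP*

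**What the plan says.** Section 7.2 a (Power Analysis) gives one set of operating characteristics for the whole table. The power statement begins "Assuming the power was 80"%, and the significance level is a one-"sided alpha of .05; we sought to determine a power analysis". The nine rows combine a true mean change in THI of 7, 10 or 15 with an SD of change of 10, 15 or 20. There are three sample-size columns: Equality (null value 0), Superiority with a threshold of 7, and Superiority with a threshold of 5.

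The Equality column is introduced as follows: "The first analysis shown is an equality test which assesses whether the mean change in THI level is different from zero". No formula is named. On the method the text says only: "This is the simplest power calculation and is usually associated with a t-test". It then explains why that test does not answer the study's question: "we would like to consider the procedure a success if the scores improve significantly by a certain amount".

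The closing paragraph takes true change 15 with SD 15 and carries forward two sizes. For threshold 5, "a difference greater than or equal to 5 can be detected using 16 subjects"; for threshold 7 it gives 24. The Study Summary separately states "Target subject accrual: 100", and the documents do not derive that figure from the table.

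**The concern.** Two features of the Equality column look wrong on a plain reading.

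- **It disagrees with itself.** The power of a one-sample test of a mean depends only on change/SD, n and alpha. Change 10 with SD 10 and change 15 with SD 15 are both a standardised effect of 1.0, yet the column prints 6 for one and 4 for the other. No single alpha and power can give both.
- **It disagrees with its neighbour.** At effect 0.667 it prints 12 (change 10, SD 15), while the threshold-5 column prints 16 for the same effect (change 15, SD 15: 10/15). At effect 0.5 it prints 19 (change 10, SD 20), while the threshold-5 column prints 27 twice.

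If the trial had been sized from this column it would have been underpowered. Four subjects at change 15, SD 15 would give 46% power instead of 80%.

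**Working it through.** **Inputs** (all from section 7.2 a, except the accrual of 100 from the Study Summary): power 0.80; one-sided alpha .05; true change 7, 10, 15; SD 10, 15, 20; null values 0, 7 and 5.

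**Formula.** Let d = (true change − null value)/SD. The required n is the smallest for which a noncentral t variable with n − 1 degrees of freedom and noncentrality d√n exceeds the upper 5% point of central t with probability at least 0.80.

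**Step 1: reproduce the plan's own figures.**

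- Threshold 7 gives 71, 156, 277, 12, 24, 41. All six match.
- Threshold 5 gives 156, 350, 620, 27, 58, 101, 8, 16, 27. Eight of nine match. The table prints 619 where this gives 620, and power at 619 is 79.97%.
- The two concluding sizes: d = (15 − 5)/15 = 0.667 with n = 16 gives 81.6% power; d = (15 − 7)/15 = 0.533 with n = 24 gives 81.3%.

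So 14 of 15 Superiority entries match exactly. A normal approximation matches only one of the 15 (the 619). The table therefore points to a one-sample t-test as its own method.

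**Step 2: apply the same test to the Equality column** (null value 0, d = change/SD).

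| Change/SD | d | Printed n | Power at printed n | Required n |
|---|---|---|---|---|
| 7/10 | 0.700 | 11 | 69.7% | 15 |
| 7/15 | 0.467 | 22 | 68.2% | 30 |
| 7/20 | 0.350 | 38 | 68.2% | 52 |
| 10/10 | 1.000 | 6 | 67.7% | 8 |
| 10/15 | 0.667 | 12 | 69.8% | 16 |
| 10/20 | 0.500 | 19 | 67.4% | 27 |
| 15/10 | 1.500 | 4 | 73.5% | 5 |
| 15/15 | 1.000 | 4 | 46.1% | 8 |
| 15/20 | 0.750 | 6 | 47.6% | 13 |

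All nine entries are too small.

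**Step 3: is this only a matter of formula?** The normal approximation, n = (SD × (1.645 + 0.842)/change)², rounded up, gives 13, 29, 51, 7, 14, 25, 3, 7, 11. Eight of nine printed entries are still too small; only change 15, SD 10 is adequate (4 printed, 3 needed). Reading a difference from zero as two-sided .05 widens the gap: the t-test then needs 19, 39, 67, 10, 20, 34, 6, 10, 16.

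**Step 4: a possible source.** A t-test at one-sided .10 and 80% power gives 11, 22, 38, 6, 12, 19, 4, 6, 9. The first seven agree with the table; the last two are printed as 4 and 6. At the same .10, a true change of 20 with SD 15 and 20 would give 4 and 6. That pattern suggests a different alpha setting plus two rows carried over from another effect size. The documents do not say so, and this remains inference.

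**Step 5: does anything rest on the column?**

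- The concluding 16 and 24 are Superiority entries, and both reproduce (step 1).
- The largest correct Equality size is 52 one-sided, or 67 two-sided. Both are below 100.
- With 100 subjects, the lowest one-sided Equality power in the table, at change 7 and SD 20, is 96.6%.

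**The case for a change.** The best case for a correction is that the column stands in the current plan under a heading of 80% power and alpha .05 that it does not meet. The check does not depend on an outside convention: the benchmark is the method that the table's other columns reveal, and the 6-against-4 conflict at effect 1.0 holds whatever alpha is assumed. PDF extraction is an unlikely explanation, because the Superiority entries in the same rows reproduce. A reader who took a size from this column would be misled, and the repair would cost only a table edit, with no patients and no design change.

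All of that stands as arithmetic. What it lacks is a consequence. The only route to harm is someone planning from the Equality column, and section 7.2 a itself steers away from that by defining success as improvement beyond a margin. The comparisons across columns also add less than they seem to: if the column was run at a different alpha, they restate the same discrepancy and are not further errors. Two gaps, 6 against 8 and 4 against 5, are no more than two patients.

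**Conclusion.** The Equality column is misprinted or was run at a setting other than the one stated. At one-sided .05 the printed sizes give 46% to 74% power instead of 80%, and the shortfall per entry runs from 1 subject (4 against 5) to 14 (38 against 52). No change to the plan follows. The column is illustrative, the text discards the test it represents, the two concluding sizes are right, and the accrual target is above every correct Equality size. Correcting or deleting the column would not alter the number enrolled, the analysis or what the trial can conclude.

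This rests on two assumptions: that the one-sample t-test inferred from the Superiority columns is the intended method, and that 16, 24 and 100 are the only sizes the trial relies on. The first affects only the size of the discrepancy, since the normal approximation leaves eight of nine entries short as well. The conclusion covers the Equality column alone. It does not address how 100 was chosen, which the documents do not explain, and several Superiority entries (101 to 619) exceed 100.

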#### b Data Analysis

THI, TFI and Tinnitus VAS scores will be analyzed based on numeric change over time after each promontory stimulation procedure. Data from the Audiograms / DPOAE will be assessed to ensure no baseline change in hearing has occurred as safety precautionary measures.

The NEO PI will be evaluated to determine correlation between tinnitus improvement scores and baseline personality assessment. Results of the NEO PI will not be used to screen for enrollment.

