### 4 STUDY DESIGN

#### 4.1 General Design

1. Experimental approach: adult patients with normal to moderate hearing loss and disruptive intractable asymmetric tonal tinnitus will be recruited for electrical promontory stimulation testing.
2. Candidate subjects will undergo a temporal bone Computed Tomography (CT) scan, contrast enhanced head Magnetic Resonance Imaging (MRI), audiogram with immittance testing, pitch and level matching of tinnitus, Distortion Product Otoacoustic Emissions (DPOAE) and Auditory Brainstem Response (ABR) testing prior to promontory stimulation. Head MRI, DPOAE, audiogram and immittance testing are considered clinically routine for assessment of asymmetric tinnitus. Temporal bone CT, ABR, tinnitus pitch, level matching, masking levels and residual inhibition testing are not standard clinical assessments for asymmetric tinnitus. In addition, subjects will complete the Tinnitus Handicap Inventory (THI), Tinnitus Functional Index (TFI) and Tinnitus Visual Analog Scale (VAS)-L (loudness) and Tinnitus VAS-A (annoyance) questionnaires three separate times within the 10 days prior to promontory stimulation testing. Additional testing for comorbid anxiety and depressive conditions will be a screening Generalized Anxiety Disorder (GAD7), Patient Health Questionnaire (PHQ8), and short Health Anxiety Inventory (HAI-S). The NEO Personality Inventory (NEO PI) will be administered to provide baseline information. The initial session of promontory stimulation will define safety stimulation parameters, with a continual treatment after defining these parameters. After treatment is completed, the patient will complete the THI, TFI, and Tinnitus VAS-A and Tinnitus VAS-L immediately prior to stimulation, during stimulation, and following completion of stimulation at 10-minutes, 1-hour, 24-hours, 48-hours, and 1-week (or prior to the next scheduled stimulation treatment, whichever occurs first) following completion of stimulation. There will also be a “recall survey” in which patients will recall the time and feeling that their tinnitus felt in the week after the stimulation procedure. In addition, pitch and level matching of tinnitus will be completed prior to the first promontory stimulation session and after the last session. Each patient

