#### **4.2 Primary Study Endpoints**

The primary study endpoints include tinnitus relief based upon questionnaires and tinnitus matching, tactile and auditory feedback, and the perception of discomfort during stimulation.

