## 6 STUDY PROCEDURES

### 6.1 Pre Visit Evaluation

Eligible subjects will be identified for inclusion at the time of referral. The study coordinator or departmental research staff will confirm compliance with initial inclusion and exclusion criteria. Informed consent will then be obtained. Then initial screening documentation, including THI, TFI, Tinnitus VAS-A and VAS-L, GAD7, GHQ, PHQ8, NEO-PI, and patient history will be reviewed.

If the patient is being seen in the Otolaryngology clinic for an alternative chief complaint, but a screening review of systems identified significant tinnitus, one of the members of the research team will be available for screening consultation and may provide informed consent at that time. A copy of the consent form will be provided to the patient to keep, and a copy will be filed and stored. Once enrolled, the THI, TFI, Tinnitus VAS-A and VAS-L, GAD7, GHQ, PHQ8 and NEO-PI scores of the subject will be recorded by the research staff.

If the patient is unable to schedule a Pre Visit Evaluation, consent may then be mailed (either via the postal service or electronically through PTRAX) to the patient. The consenting provider will meet with the patient by phone or video visit and read through the consent form with the potential participant. If desire to proceed, signed consent form will be returned either electronically or by mail and screening documentation will be provided to the patient. The THI, TFI, Tinnitus VAS-A and VAS-L, and Pain VAS, GAD-7, PHQ-8, and/or the NEO-PI may be mailed or sent electronically to the subject after consent so they may do these eligibility screening surveys at home without making a trip to Mayo Clinic. They will return these screening surveys which will be scored, and if the scores qualify, the subject will come in person for a clinical visit and the rest of the initial screening surveys, if they did not do the whole set at home.

After eligibility is determined, subject will complete study questionnaires (THI, TFI, and Tinnitus VAS-A and VAS-L) at three separate time periods in conjunction with the first clinical visit.

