#### **6.2.1 Transtympanic Cochlear Promontory Stimulation**

- a. At the first, second and third clinical appointment, the promontory stimulation equipment (Cochlear Corporation Nucleus Promontory Stimulator Z10012®; Cochlear Corporation, Melbourne, Australia) will be used. The initial session of promontory stimulation will define optimal stimulation parameters (i.e., current level, and frequency), where maximal tinnitus suppression occurs with minimal or no auditory percept. Stimulus amplitude will be increased slowly to establish threshold and maximum acceptable loudness. As an internal control function, testing will include a run of “on-off” simulations blinded to the subject, with patient blinded status to the “off” or “on” position of the stimulation machine. After these parameters are established, the patient will complete the THI, TFI, and VAS immediately prior to stimulation, during stimulation, and following completion of stimulation at 10-minutes, 1-hour, 24-hours, 48-hours, and 1-week following completion of stimulation (or prior to the next scheduled session of promontory stimulation, whichever occurs sooner), in addition to the recall survey, which is completed after a time period of one week (or prior to the next scheduled session of promontory stimulation, whichever occurs sooner). In addition, pitch and level matching of tinnitus will be completed immediately prior to the first promontory stimulation session and after the last session. Each patient will undergo three successive treatments separated by 7 days (+14/- 2 days). Prior to each treatment, the patient will receive an audiogram and DPOAE testing to document interval safety. At the conclusion of the study, subjects will be asked about their willingness to undergo surgical implantation of a device capable of long-term scheduled or on-demand electrical stimulation for tinnitus suppression.

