- b. The Cochlear Corporation Nucleus Promontory Stimulator Z10012 (Cochlear Corporation, Melbourne, Australia) will deliver stimulatory electric pulses. The stimulation will be delivered to the target sites using a transtympanic electrode kit, which contains a monopolar transtympanic needle electrode referenced to a surface electrode to be placed on the patient’s forehead. The tympanic membrane will be visualized with otomicroscopy with the patient in the supine position. Phenol will be applied to the tympanic membrane for local anesthesia. If residual irritation is perceived, EMLA cream will be used in the external auditory canal. The transtympanic electrode needle will be guided through the external canal aiming for the posteroinferior quadrant of the tympanic membrane. The needle will be stabilized in the ear canal using cotton packing or hearing aid mold putty and adhesive tape. Initially, an electrode impedance test will be performed

to validate proper placement and electrical contact of the electrodes. An indicator light will denote when impedances are not acceptable. If impedance values are not acceptable, a gentle repositioning of the proximal end of the needle electrode may be employed to ensure proper placement on the promontory. Otherwise, the needle electrode will be removed and reintroduced. Once proper electrical contact is validated, a calibration session to assess optimal stimulation parameters for the therapeutic session will be carried out using a range of 0 to 1 mA for pulse frequencies 100 Hz, 800 Hz and 1600 Hz. For each stimulus frequency, current level will be gradually increased to determine the following perceptual parameters: 1) Detection threshold or minimum threshold: first detection of the electrical stimulus (tactile or audible) as reported by the patient. 2. Maximum acceptable loudness level or discomfort level: when the applied current is perceived as loud but not uncomfortable. 3. The effective stimulation level will be determined to be 80% of the discomfort level or at minimum the minimum threshold level. The total duration of the electrical stimulation (at the optimal level) in each session will be ~30-60 minutes.

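### The planned subject-blinded on-off run has no stated outcome or analysis, so efficacy in Section 7.2b rests on uncontrolled change in self-reported scores

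*Combined protocol and SAP*

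**What the plan says.** Section 7.2b gives the efficacy analysis in one sentence: "THI, TFI and Tinnitus VAS scores will be analyzed based on numeric change over time after each promontory stimulation procedure". The only other analysis there that uses efficacy scores is a correlation of improvement with the NEO PI. The power section (7.2a) works with mean THI change in one group, compared with 0, 5 or 7 points, and says "we would like to consider the procedure a success if the scores improve significantly by a certain amount".

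Section 6.2.1a provides for a blinded comparison: "As an internal control function, testing will include a run of" on and off conditions, with the subject unaware of the position of the machine. The run is described with the parameter-finding phase. The THI, TFI and VAS are completed around the treatment stimulation, once the parameters are set. No section says what is recorded in the run, how many epochs it has, in what order they come, or how on is compared with off.

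Section 4.2 lists the primary endpoints as "tinnitus relief based upon questionnaires and tinnitus matching, tactile and auditory feedback, and the perception of discomfort during stimulation". Perception of current is therefore assessed, and Section 6.2.1b defines the minimum threshold as "first detection of the electrical stimulus (tactile or audible) as reported by the patient". No on/off guess is planned.

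Scores are taken immediately before, during, and "following completion of stimulation at 10-minutes, 1-hour, 24-hours, 48-hours, and 1-week" in each of three sessions. Section 4.1 also has subjects complete the "questionnaires three separate times within the 10 days prior to promontory stimulation testing".

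**The concern.** Subjects know that they are receiving a procedure for their tinnitus, and the outcomes are their own ratings. Expectation, natural fluctuation and repeated questioning can all lower such scores without any effect of the current. A one-sample test of change cannot separate these from a device effect, and a larger sample only makes a non-specific fall easier to declare a success.

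The protocol recognises the need for a control, because it calls the on-off run one. With no outcome or analysis specified, the run need not produce any data that bear on efficacy, and ratings not taken at the time cannot be recovered later. The primary objective is to characterise efficacy, and the results are meant to inform an implantable device, so attribution to the current matters.

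**Working it through.** **Inputs.** From 7.2a: one-sided alpha 0.05, power 80%, SD of THI change 15, thresholds 7 and 5. From the Study Summary: target accrual 100. Assumed, because the documents give no figure: the size of the non-specific THI fall, the SD of the on-minus-off VAS-L difference, the amount of carry-over, and the correlation between repeated scores.

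**Step 1, the plan's own figures.** For a one-sample t-test with true change d and threshold T, power = P[t′(n−1, δ) > t(0.95, n−1)], where t′ is non-central t and δ = (d − T)√n / 15. The smallest n reaching 80% is:
- d = 15, T = 7: 24 (81.3%; 23 gives 79.8%)
- d = 15, T = 5: 16 (81.6%; 15 gives 79.1%)
- d = 10, T = 7: 156
- d = 10, T = 5: 58

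All four agree with the table. The calculation is thus a single-group change against a fixed number, with no control term.

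**Step 2, pass rate with no device effect.** Use the same formula with d replaced by an assumed non-specific fall m. For example, m = 10, T = 7, n = 24 gives δ = 3 × 4.899 / 15 = 0.98 against a critical value of 1.714, hence 24%.

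| Threshold | n | Assumed fall and pass rate |
|---|---|---|
| 7 | 24 | 8: 9%; 10: 24%; 12: 48% |
| 7 | 100 | 8: 16%; 10: 63%; 12: 95% |
| 5 | 16 | 7: 13%; 10: 36% |
| 5 | 58 | 7: 26%; 10: 81% |
| 5 | 100 | 7: 37%; 10: 95% |

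A fall equal to the threshold passes 5% of the time, and a smaller one less often.

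**Step 3, what the on-off run could deliver.** Take one on-minus-off VAS-L difference per subject, with SD s between 1 and 3. The 95% CI half-width is t(0.975, n−1) × s / √n: 0.42 to 1.27 points at n = 24 and 0.20 to 0.60 at n = 100. The difference detectable with 80% power (two-sided 5%) is 0.60 to 1.79 points at n = 24 and 0.28 to 0.85 at n = 100.

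**Step 4, carry-over.** The Background says that suppression usually extends shortly beyond stimulation. Suppose two on and two off epochs in random order (six equally likely orders), with each off epoch keeping a fraction c of the suppression in the epoch before it.
- Nothing precedes the run: the mean residual in off epochs is (3c + c²)/6. For c = 0.25 this is 0.135, so 86.5% of the true difference remains. For c = 0.5 it is 0.292, so 70.8% remains.
- Stimulation immediately precedes the run: the mean residual is 0.75c + 0.25c², so 79.7% or 56.3% remains.

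**Step 5, choice of time point.** Six scores per session (during, plus five afterwards) over three sessions make 18 for THI. Taking the best of 18 turns a 5% error into about 14% to 33% for pairwise correlations of 0.9 to 0.5 (20,000 simulated trials at n = 24; n = 100 is similar).

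**The case against.** Several objections have force.

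- The on-off run can be read as a check on what subjects report while parameters are being set. That is a legitimate use, so the documents do not support the inference that it controls nothing. What stands is narrower: its result has no stated route into the efficacy analysis.
- The pass rates rest on assumed non-specific falls, and 7.2b adopts neither a test nor a threshold. If the 7-point test is used, a fall of 7 points or less passes at most 5% of the time, so that threshold gives real protection. A reader might take the larger percentages as the trial's expected false-success rate; the documents do not support that.
- The blind may fail. Section 6.2.1b sets the effective level at 80% of the discomfort level or at least the minimum threshold, which is defined by first detection. Section 6.2.1a, however, seeks little or no auditory percept, and the level used in the on epochs is not stated. Unblinding is therefore a risk rather than a certainty, but it limits what the contrast can show.
- A short run during parameter setting may not represent a treatment of about 30 to 60 minutes. This stands, and it confines the contrast to acute effect.
- A reader might also count the lack of a named reference score and main time point as an equal fault. Each session's own pre-stimulation score is the natural reference. Choosing afterwards between the session-1 pre-score and the mean of the three earlier sets gives only about 6% to 8% error under the assumptions examined. Those sets, for which Section 6.1 says "After eligibility is determined, subject will complete study questionnaires (THI, TFI, and Tinnitus VAS-A and VAS-L) at three separate time periods", could be up to 59 days old by the last one-week score (10 + 21 + 21 + 7). This is mostly missing detail.

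**Conclusion.** The concern holds for the on-off run. Followed as written, the plan gives an uncontrolled efficacy conclusion and leaves its one blinded contrast without specified data or analysis. The size of the resulting error cannot be known from the documents. Under the power section's tests with SD 15, it ranges from 5% or less when the non-specific fall does not exceed the threshold to 95% for a 12-point fall against the 7-point threshold with 100 subjects.

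This does not make the single-group design invalid, nor does it show that a device effect is absent. The contrast, once recorded, would support a statement about acute effect only; carry-over would shrink it and a broken blind could inflate it. Naming a main time point is worthwhile but secondary. The point should be fixed, because the remedy is cheap and uses a run already planned.

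**What to change.** 1. **Section 6.2.1a.** Fix the number of on and off epochs in advance and run them in a pre-specified randomised order. State whether the run follows calibration stimulation. In each epoch record VAS-L, the subject's on/off guess, and whether current was felt or heard.
2. **Section 7.2b.** Report the paired on-minus-off VAS-L difference with a 95% CI as the blinded evidence, for acute effect only. Show guess accuracy and felt/heard rates beside it as a check on the blind. Do not use correct guessing to define an efficacy subgroup, since real relief can itself prompt an on guess. State that carry-over biases the difference towards zero.
3. **Section 7.2b.** Describe the THI, TFI, tinnitus-matching and later VAS changes as uncontrolled.
4. **Optional.** Name one main session and time point before any analysis, with the score during stimulation allowed as the choice. Keep each session's own pre-score as the reference and use the mean of the three post-eligibility sets as a sensitivity baseline.

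The cost is three short answers per epoch and some analysis wording; the baseline sets are already collected. The downside is a more modest efficacy statement if on and off do not differ or the blind fails.

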will undergo three successive treatments separated by 7 days (+14/- 2 days). Prior to each treatment, the patient will receive an audiogram and DPOAE testing to document interval safety. At the conclusion of the study, subjects will be asked about their willingness to undergo surgical implantation of a device capable of long-term scheduled or on-demand electrical stimulation for tinnitus suppression.

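### Section 7.2b does not say how a subject's three sessions are combined, or which session and time point is tested against the 5- or 7-point THI margin

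*Combined protocol and SAP*

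**What the plan says.** Section 4.1 (General Design) states that each patient "will undergo three successive treatments separated by 7 days", with a window of +14/-2 days; section 6.2.1 repeats this. Section 7.1 has THI, TFI, VAS-A and VAS-L scored before stimulation, during it, and at 10 minutes, 1 hour, 24 hours, 48 hours and 1 week after it. That is up to six scores per scale per session after the pre-stimulation score, or 18 per subject.

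The analysis of these scores in section 7.2b is one sentence: "THI, TFI and Tinnitus VAS scores will be analyzed based on numeric change over time after each promontory stimulation procedure". It names no test, model, primary session or primary time point, and no way to combine sessions or allow for correlation within a subject. Section 4.2 lists questionnaire-based relief as a primary endpoint without adding to this.

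Section 7.2a uses a one-sided alpha of 0.05 and 80% power. Of the equality test it says "This is the simplest power calculation and is usually associated with a t-test". It then compares the mean THI change with a margin: "if we believe our true mean change to be a 15 THI points with a SD of 15", then "a difference greater than or equal to 5 can be detected using 16 subjects", while to "detect a mean change greater than 7 we would need 24 subjects". It does not say which session or time point supplies the change.

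**The concern.** Section 7.2a treats a mean THI change beyond a margin as success, so the trial's conclusion rests on one comparison. Yet the data offer three sessions and six time points per session for that comparison, and the plan chooses none. Two things are at stake.

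- **Precision.** If the test uses one session, the other two add nothing to the estimate of the mean effect, although they are already collected.
- **Error control.** If every session is tested and success at any one counts, the chance of a false success exceeds 5%. With no rule written down, the choice could be made after the data are seen.

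**Working it through.** **Inputs from the documents.** Power 80%, one-sided alpha 0.05, SD of THI change 15, true change 15 or 10, margin 7 or 5 (section 7.2a); three sessions per subject (4.1, 6.2.1); target accrual 100 (Study Summary).

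**Assumptions.** The between-session correlation of a subject's changes, rho, is not given; I take 0.3 to 0.9. I also assume the same SD and mean effect at each session, and complete data.

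**Step 1: reproduce the plan's figures.** One-sample t-test, power from the noncentral t with noncentrality (true change − margin)/SD × √n.

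- Margin 7: (15 − 7)/15 × √24 = 2.61, power 0.813. The smallest n reaching 80% is 24, as stated.
- Margin 5: (15 − 5)/15 × √16 = 2.67, power 0.816. The smallest n is 16, as stated.
- True change 10, SD 15: 58 for margin 5 and 156 for margin 7, both as stated.

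The sizing therefore uses one change per subject and takes nothing from the second and third sessions.

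**Step 2: use all three sessions with the subject as the unit.** SD of a subject's mean change = 15 × √((1 + 2·rho)/3). For rho = 0.5 this is 15 × √(2/3) = 12.25.

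| rho | SD of mean | n needed (true 15, margin 7) | Power, n=24 (true 15, margin 7) | Power, n=100 (true 10, margin 7) |
|---|---|---|---|---|
| one session | 15.00 | 24 | 81% | 63% |
| 0.3 | 10.95 | 14 | 97% | 86% |
| 0.5 | 12.25 | 16 | 93% | 79% |
| 0.7 | 13.42 | 19 | 88% | 72% |
| 0.9 | 14.49 | 22 | 84% | 66% |

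**Step 3: one session at the target accrual, for the scenarios in bold in 7.2a.** At n=100, true change 10 with margin 5 has noncentrality 5/15 × 10 = 3.33 and power 95%. True change 15 with margin 7 has noncentrality 8/15 × 10 = 5.33 and power above 99.9%; margin 5 is higher still.

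**Step 4: error if success at any session counts.** With independent sessions it is 1 − 0.95³ = 14.3%. By simulation with 24 subjects it is 13%, 12%, 10% and 8% at rho 0.3, 0.5, 0.7 and 0.9. A single pre-named session, or the subject mean over three sessions, stays at about 5%.

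**The case against.** - **The sentence in 7.2b names a quantity, not a method.** A joint model of change within and across sessions would fit its wording. This stands, and it is why the point is one of missing specification.
- **A reader might infer that sessions will be pooled as independent observations.** That would be a real error: the one-sided level would be about 10-16% for rho 0.3-0.9. But nothing in the documents plans it, and 7.2a counts subjects. The inference is not supported.
- **A reader might infer that two thirds of the data are discarded.** The documents do not say so. Analysis after each procedure would report every session, and a subject who misses the third still counts in the first two. What is lost is precision for an overall effect.
- **The gain may be small.** At rho 0.9, power at n=24 rises only from 81% to 84%. High correlation is plausible if all three changes are taken from the shared pre-study scores in section 4.1; the plan does not say which baseline applies. This stands.
- **Power is ample at n=100.** This stands for the scenarios in bold (step 3). True change 10 with margin 7, where the gain is visible, is not in bold.
- **Sessions may not be exchangeable.** The first session also sets the stimulation parameters (6.2.1), the Background says residual inhibition can last hours to days, and sessions may be 5 days apart. An average is therefore a choice of estimand. This is fair, and a reason to state the choice and show the session estimates beside it.
- **A joint model can itself be wrong.** With only a subject random intercept, scores within a session are treated as independent given the subject. In a simulation of 24 subjects, 3 sessions and 6 times, with session-within-subject variance assumed at 10-35% of the total, a nominal 5% test of the session effect rejected 21-54% of the time under no effect. The covariance must therefore be specified.

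**Conclusion.** The concern holds as a gap in specification with a moderate cost. The plan gives no rule for combining three sessions per subject and does not name the session or time point tested against the margin. Separate session tests are valid one at a time but less precise; success at any session would carry a one-sided error of about 8-13% (rho 0.9-0.3).

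Over the same range, averaging sessions raises power from 81% to 84-97% at n=24 (true 15, SD 15, margin 7) and from 63% to 66-86% at n=100 (true 10, SD 15, margin 7). These figures rest on an assumed correlation, equal session effects and complete data.

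A reader might conclude that the sample sizes of 24 and 16 are invalid. They are not: both reproduce, and both are conservative if sessions are averaged under these assumptions. At n=100 the main benefit is a test fixed in advance.

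**What to change.** In section 7.2b:

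1. Name one post-stimulation time point for the THI margin test, the margin (5 or 7), and the baseline from which change is measured.
2. Analyse all three sessions jointly in a mixed model of change, with fixed effects for session, time point and pre-stimulation baseline. Centre the baseline so that the estimate is the mean change.
3. Allow correlation both between and within sessions, by subject and session-within-subject random effects or an unstructured covariance. Unstructured over all 18 scores has 18 × 19/2 = 171 parameters, so it is practical mainly for the three sessions at the named time point (3 × 4/2 = 6).
4. As a simpler alternative, test each subject's mean change over the three sessions, with a rule for subjects who miss one.
5. Make the session-averaged effect at the named time point, with its confidence interval against the margin, the single primary test. Report session-specific estimates as secondary.

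The cost is a few sentences and a little more analysis work, with no added subjects, visits or measurements. A likelihood-based model also keeps subjects who miss a session, which matters because section 5.4 allows withdrawal at any time. The downside is that an average can mask differences between sessions, notably because the first also sets the stimulation parameters; the session-specific estimates would show them.
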